13.3 Statistical Analysis Plan

A Statistical Analysis Plan (SAP) will be written and finalized prior to database lock. The SAP will provide a detailed description of the statistical methods and expand on the details provided in the protocol. Additional analyses may be added. Tables, listing and figures shells will also be provided.

13.4 Randomization

This is a double-blind, placebo-controlled study. The actual treatment given to individual subjects is determined by a randomization schedule. The associated treatment assignments giving details of individual subject treatment are assigned from a randomization list. After entry criteria are confirmed at the end of Visit 3, subjects will be randomized at Visit 4 (Day 1) using a 3:1 ratio to receive either the Viaskin® Milk or placebo.

13.5 Analysis Populations

All the analysis populations will be identified and finalized in the SAP.

13.5.1 Safety Population

The safety population will be comprised of all subjects who are randomized and received at least one dose of study drug. This population will be used to assess comparative safety information.

13.5.2 Intent-to-treat Population

The intent-to-treat (ITT) population (full analysis set) will be comprised of all subjects who are randomized. This population will be used to assess comparative efficacy information.

13.5.3 Per Protocol Population

The per protocol (PP) population will include all subjects in the ITT population who do not have pre-defined major deviations from the protocol that may affect the primary (and secondary) endpoints (for instance, subjects who have not gone through the third upper endoscopy and biopsy at the end of treatment, subjects with a compliance below 80% etc.) The deviations to consider will be listed more exhaustively in the SAP. The PP population will be used to perform confirmatory analyses of the primary efficacy evaluation.

13.6 Statistical Methods

The statistical analyses for the entire study as further outlined in the SAP will be included in the Clinical Study Report for this protocol. The SAP will give a detailed description of the summaries and analyses (primary and secondary) that will be performed and clearly describe when these analyses will take place. The SAP will be finalized prior to database lock to preserve the integrity of the statistical analysis and study conclusions.

All pre-defined statistical analyses will be performed after the database is released for unblinding. Statistical analyses will be performed using SAS® Version 9.1 or higher (SAS Institute, Cary, NC

27513)

Descriptive statistical analysis of all data obtained will be conducted using inferential and graphical exploratory data analytic techniques. Descriptive statistics will be presented as means and standard deviations or median and interquartile ranges or minimum and maximum for continuous variables and frequency counts and percentages for categorical variables. The denominator for percentages will be the number of subjects in the population with data available unless otherwise stated.

13.6.1 Missing Data

Every attempt must be made by the Investigator to provide complete data. The primary analysis can be performed on data without imputation. However, exploratory analyses using the multiple imputation method and last observation carried forward should be utilized to assess the robustness of the data.

Analyses of primary and secondary efficacy measures will be based on the intent-to-treat (ITT) population, with missing values imputed using the last value carried forward analysis.

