8.4.3.3 Evaluations at Withdrawal

For any subject who is withdrawn before completing all study visits, the Investigator should:

- Perform an end of study visit: all subjects who are withdrawn early from the trial will undergo the procedures planned for Visit 17 (see Section 9). End of study visits will be performed no later than 2 weeks after withdrawal/discontinuation.
- Complete all appropriate subject Diary and eCRF pages, providing the date and explanation for the subject's withdrawal/discontinuation.
- When indicated, arrange for appropriate follow-up and/or alternative medical care of the discontinued subject.

If the subject fails to attend for a scheduled end of study visit, there will be at least two attempts to contact the subject via telephone and written communication. If these receive no reply, the subject will be considered lost to follow-up.

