11.8 Upper Endoscopy with Biopsy

All subjects will undergo a minimum of four upper endoscopies with biopsies during their participation in the study (two each of proximal and distal, plus any inflamed areas) as per standard clinical practice: at least two at Screening as Standard of Care (Visit 2 and Visit 3) and two at the end of each treatment period as Research (Visit 10 and Visit 16). The results of additional SOC endoscopies will be allowed to assess eligibility, if the endoscopies are required for clinical care purposes. The samples will be processed by the Department of Pathology at The Children's Hospital of Philadelphia and the number of eosinophils will be counted using hematoxylin and eosin stain. The handling of samples will be done following ASGE Standard on Endoscopic Mucosal Tissue Sampling.⁶⁷

Upper endoscopy will be scored using a validated standardized measure.⁵⁷ The measure examines four major esophageal features (rings, furrows, exudates and edema) and the presence of minor features of narrow caliber esophagus, feline esophagus, stricture and crepe paper esophagus. The features are graded:

- Rings (0-none, 1-mild, 2-moderate, 3-severe)
- Exudates (0-none, 1-mild, 2-severe)
- Furrows- (0-mild, 1-present)
- Edema- (0-mild, 1-present)
- Stricture (0-mild, 1-present)
- Crepe paper esophagus (0-mild, 1-present)

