### **3.3 Missing data**

Every attempt must be made by the Investigator to provide complete data. The primary analysis can be performed on data without imputation. However, exploratory analyses using various imputation techniques (i.e., last observation carried forward (LOCF)) will be utilized to assess the robustness of the data. Analyses of secondary efficacy measures will be based on the intent-to-treat (ITT) population with missing values imputed using the last value carried forward analysis.

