**Table 7 specification**

Repeat with ITT population and PP population with LOCF separately as Table 7A and 7B, respectively.

Table 8. Summary Statistics for Total Esophageal Endoscopy Score (Secondary Efficacy Endpoint)

	All	Viaskin® milk	Placebo	Median Difference (95% CI) #
Total esophageal endoscopy score				
Baseline				
Visit 10				
Visit 16				
Change from baseline to visit 10				xx (xx, xx)
Change from baseline to visit 16				xx (xx, xx)

Values will be expressed as n, n missing, mean  $\pm$  SD, median (IQR) range.  

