### Table 13 specification

Repeat on ITT population and PP population separately as Table 13A-1 and Table 13A-2 as well as Table 13B-1 and Table 13B-2, respectively.

Table 14. Summary Statistics for Eosinophilic Esophagitis Quality of Life Score (Secondary Efficacy Endpoint)

	All	Viaskin® milk	Placebo	Median Difference (95% CI) #
Quality of life score				
Baseline				
Visit 10				
Visit 16				
Change from baseline to visit 10				xx (xx, xx)
Change from baseline to visit 16				xx (xx, xx)

Values will be expressed as n, n missing, mean  $\pm$  SD, median (IQR), and range..  

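### For a double-blind dropout, LOCF of biopsy, endoscopy-score and quality-of-life endpoints can carry only a pre-treatment screening value, normally milk-free, or else it fills nothing

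*Protocol*

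**What the plan says.** **Imputation rule.** Protocol 13.6.1 first says "The primary analysis can be performed on data without imputation" and lists multiple imputation and LOCF as exploratory. It then ends by saying that analyses of "primary and secondary efficacy measures will be based on the intent-to-treat (ITT) population, with missing values imputed using the last value carried forward". SAP 3.3 keeps the first statement and adds that "exploratory analyses using various imputation techniques (i.e., last observation carried forward (LOCF)) will be utilized to assess the robustness of the data". It confines the prescriptive sentence to "secondary efficacy measures will be based on the intent-to-treat (ITT) population with missing values imputed using the last value carried forward" and does not name multiple imputation.

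**Table notes.** The note to the primary table (SAP Table 7) reads "Repeat with ITT population and PP population with LOCF separately as Table 7A and 7B, respectively". The notes to the secondary tables do not mention LOCF; Table 13, for instance, says "Repeat on ITT population and PP population separately as Table 13A-1 and Table 13A-2".

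**Schedule.** Protocol 11.8 places the endoscopies as "at least two at Screening as Standard of Care (Visit 2 and Visit 3) and two at the end of each treatment period". Protocol Tables 3A and 3B put the endoscopy score and quality of life at the same four visits. On withdrawal, Protocol 8.4.3.3 says "all subjects who are withdrawn early from the trial will undergo the procedures planned for Visit 17"; the Visit 17 list in 9.13 has no endoscopy and no quality-of-life measure.

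**Entry values.** Protocol 8.4.1 requires at least 15 eosinophils/HPF on milk and 0 to 10 after at least six weeks without milk. Clinical care sets the order of these endoscopies (Table 3 footnotes), and qualifying ones may date from the preceding 12 months (8.1). The Visit 10 endpoint is measured after milk has been reintroduced.

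**The concern.** LOCF presupposes an earlier on-study value of the same kind. Here none is planned. The value carried would describe the subject before treatment and normally on the opposite diet. Under the categories in SAP 4.4.2.3, a carried 0 to 10 is always excellent or good. If clinical care reversed the screening order, the carried value is at least 15 and always poor. In both cases diet and screening order decide the subject's result, and treatment plays no part.

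The endpoints affected are the Visit 10 eosinophil counts and changes, response categories, endoscopy score, composite score and quality of life, and the same Visit 16 endpoints in double-blind dropouts. With six placebo subjects, each placebo dropout is one sixth of the control arm. Neither document says which earlier value may be carried, so two programmers could build different tables from the same text.

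**Working it through.** **1. What exists to carry**

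| Visit | Biopsy, endoscopy score, quality of life | Diet |
|---|---|---|
| 2 (screening) | yes | on milk |
| 3 (screening) | yes | milk-free |
| 4 to 9 | none | milk-free; milk restarts at Visit 9 |
| 10 | yes | on milk |
| 11 to 15 | none | depends on the Visit 10 result |
| 16 | yes | on milk |
| 17 / early withdrawal | none | not applicable |

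Planned post-randomisation values before Visit 10: zero. The symptom-triggered endoscopy (Protocol 9.12.1) follows milk reintroduction and is itself the research endoscopy, so it supplies no earlier value. The composite contains the maximum count and the endoscopy score. PEESS is listed with the quality-of-life instruments in Protocol Appendix 2. A missing Visit 16 value after an observed Visit 10 is a different case and is outside this point.

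**2. The plan's power figure**

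Protocol 13.2 gives means of 10 and 50, SD 20, 16 and 6 subjects, two-sided 0.05 and 90% power. The noncentrality is 40 / (20 × √(1/16 + 1/6)) = 4.18, and the t-test power is 97.8%, so 90% is not reproduced. With 18 completers it is 91.1% (14+4) or 94.6% (13+5). Nothing below depends on the 90%. Going from 22 randomised to 18 completed leaves four missing (18.2%), although the text says 10%.

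**3. Expected rate below 15 eosinophils/HPF**

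Assumptions: normal counts with the plan's inputs, a carried value of 0 to 10, and dropout splits (active+placebo) that the documents do not give.

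- Active: Φ((15 − 10)/20) = 0.599. Placebo: Φ((15 − 50)/20) = 0.040.
- LOCF rate = [(n − m) × p + m] / n, where m of n subjects are missing.
- Probability of a split under random dropout = C(16,a) × C(6,p) / C(22,4).

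| Four missing | Probability | Active | Placebo | Gap (points) | Relative risk of poor response |
|---|---|---|---|---|---|
| Observed cases | – | 60% | 4% | 56 | 0.42 |
| LOCF 4+0 | 0.249 | 70% | 4% | 66 | 0.31 |
| LOCF 3+1 | 0.459 | 67% | 20% | 47 | 0.41 |
| LOCF 2+2 | 0.246 | 65% | 36% | 29 | 0.55 |
| LOCF, average | – | 67% | 21% | 46 | 0.42 |

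Example, 3+1: (13 × 0.599 + 3)/16 = 0.674 and (5 × 0.040 + 1)/6 = 0.200. Average: (18/22) × 0.599 + 4/22 = 0.672 and (18/22) × 0.040 + 4/22 = 0.215. With two missing, the average is 64% versus 13%. If the screening order was reversed and a value of at least 15 is carried, 3+1 gives 13 × 0.599/16 = 49% versus 5 × 0.040/6 = 3%.

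The normal model puts 31% of active counts below zero. With lognormal counts of the same means and SD, the observed rates are 83% versus 0.2%; LOCF gives 86% versus 17% for 3+1 and 86% versus 18% on average.

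**4. Maximum count, only where LOCF is applied to it**

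Simulated t-test power, LOCF against observed cases (carried value uniform on 0 to 10):

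- 4+0: 99% against 96%
- 3+1: 94% against 95%
- 2+2: 72% against 91%
- Average over random dropout: 87% against 94%; with two missing, 93% against 96%
- ANCOVA on the milk-free baseline, average: 85% against 92%
- Lognormal counts, average: 89% against 92% on the raw scale; 91% against 99% on log(count+1)

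Average two-sided type I error stays at about 5%. Within a given split it varies: with both means set to 50 it is 8.9% for 4+0, 0.4% for 3+1, 3.8% for 2+2 and 32.8% for 1+3 (probability 0.044).

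**The case against.** The strongest reply is that the tables will be built on observed cases anyway. The shells for Tables 6, 8, 11, 12, 14 and 15 carry rows for the number missing, Table 9 reports the number of observations used, and Protocol 13.6 uses subjects with available data as the denominator unless otherwise stated. A fully imputed table would not need these. That is fair evidence of intent, but it contradicts the LOCF sentence in SAP 3.3 without replacing it.

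The effect can also be small. In the most likely split (3+1) the relative risk of poor response and the power hardly move. The SAP text reports the affected secondary endpoints as estimates with confidence intervals, and the trial is a proof-of-concept pilot. This stands, and it limits the seriousness.

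A reader might infer more: that the primary analysis itself rests on carried-forward milk-free biopsies, or that LOCF inflates false positives in favour of active treatment. The documents do not support the first, because SAP 3.3 allows the primary without imputation and makes LOCF exploratory. The last sentence of Protocol 13.6.1 and the Table 7 note conflict with that, but do not make LOCF the settled main rule. The second fails on average: under random dropout, rejections favouring active are 2.5% with four missing and 2.3% with two, against a nominal 2.5%. Nor does LOCF always hide benefit, since the gap widens in 4+0.

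**Conclusion.** The point holds for the secondary endpoints. Both documents prescribe LOCF there, and the schedule leaves only a pre-treatment value to carry, or nothing. For the primary, the defect is conflicting text plus an exploratory analysis that carries the wrong kind of value.

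The structural finding needs no assumption beyond the planned schedule; only an unscheduled endoscopy would change it for an individual. The size is illustrative. It rests on the plan's means and SD, four missing biopsies, a carried value of 0 to 10 and assumed splits, and the responder rates depend heavily on the distribution chosen. On average LOCF narrows the responder gap from 56 to 46 points (normal model) and, where applied to the maximum count, lowers t-test power from 94% to 87%. When dropout differs by arm, the distortion can go either way. No size was worked out for endoscopy score, composite, quality of life or the relative risk of excellent response. It should be fixed before database lock.

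**What to change.** 1. In Protocol 13.6.1, SAP 3.3 and the Table 7 note, state that the primary analysis uses all randomised subjects with a Visit 10 biopsy, as randomised, without imputation. Delete the LOCF wording from the Table 7 note. The per-protocol set excludes subjects without the third endoscopy (SAP 4.1), so it has nothing to fill.
2. State that no screening value is carried forward for Visit 10 eosinophil counts, response categories, endoscopy score, composite score, PEESS or quality of life, nor for the same Visit 16 endpoints in double-blind dropouts. Report these on observed cases.
3. The symptom score is collected at each visit, but its values before Visit 10 are normally milk-free too. Do not carry a milk-free value into the on-milk Visit 10 score. Make observed cases the main analysis and label any LOCF result as sensitivity.
4. For sensitivity, restore to the SAP the multiple imputation named in Protocol 13.6.1, conditional on the on-milk screening count. Also show Table 13A with a missing Visit 10 biopsy counted as poor, beside the observed-case table.

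The cost is wording and minor programming. Multiple imputation will be imprecise with about six placebo subjects. Counting missing as poor is itself a single imputation and gives less favourable rates: for 3+1, 49% versus 3% below 15, and a relative risk of poor response of (1 − 0.486)/(1 − 0.033) = 0.53, against 0.42 observed.

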13.6.2 Demographic and Baseline Data

Descriptive statistics will be produced as means, standard deviations, medians, and ranges for continuous demographic and baseline characteristics (including age, height, weight and maximum Esophageal Eosinophil Count) and frequency counts and percentages for the categorical demographic and baseline characteristics (including race, ethnicity, medical history) will be produced by treatment group and overall. Distribution of the continuous outcomes will be evaluated using histograms. Transformation of some of these continuous variables will be performed wherever deemed more appropriate. The balance of the demographic and baseline measures between the treatment groups will be compared using two-sample t-tests or the Mann-Whitney tests as appropriate for continuous variables and the chi-square tests for categorical variables.

All individual subject demographic and baseline characteristic data will be listed.

13.6.3 Subject Disposition

Subject disposition will be summarized for the intention-to-treat population. The number and percentage of subjects randomized, subjects in each study population (Safety, ITT, PP), and subjects who received study medication, who completed the double-blind period, who discontinued the double-blind period, and the primary reason for discontinuation from the double-blind period will be tabulated by treatment group and overall.

13.6.4 Efficacy

13.6.4.1 Primary Efficacy Variable

The primary efficacy endpoint is defined as the maximum esophageal eosinophil count on all specimens obtained on the biopsy at end of double-blind treatment (Visit 10), after milk reintroduction at Visit 9. The null hypothesis is that the mean maximum esophageal eosinophil

count in active treatment group is the same as that in the placebo group. This hypothesis will be evaluated using an analysis of covariance (ANCOVA) model with treatment group, baseline patient's maximum esophageal eosinophil count, and age group (4-11 years old versus 12-17 years old) as covariates. The null hypothesis will be tested against the alternative hypothesis that the results are different in each treatment group at the 0.05 significance level. The least square means for the treatment groups, difference in least square means between the treatment groups, effect size calculated as the absolute difference in least square means between active group and placebo divided by the root mean square, and p-value for difference between treatment groups will be presented.

13.6.4.2 Secondary Efficacy Variables

The following secondary efficacy endpoints will be assessed:

Esophageal Eosinophil Count

The mean Esophageal Eosinophil Count of all specimens obtained at the end of treatment as well as the change from baseline will be summarized by treatment group.

The null hypothesis that the mean Esophageal Eosinophil Count eliciting doses at the end of treatment are the same in each treatment group will be analyzed using ANCOVA model with treatment group, baseline patient's mean esophageal eosinophil count, and age group (4-11 years old versus 12-17 years old) as covariates. This null hypothesis will be tested against the alternative hypothesis that the results are different in each treatment group at the 0.05 significance level.

Esophageal Endoscopy Score

The total score for each subject will be calculated (for endoscopy) and summary statistics will be presented for each treatment group at baseline and the end of study. This will be based on each symptom being graded for severity as 0, 1, 2 or 3 (respectively none, mild, moderate and severe). The total scores at the end of treatment between two treatment groups will be examined using ANCOVA model with treatment group, baseline patient's total score, and age group (4-11 years old versus 12-17 years old) as covariates. The change from baseline to end of treatment will also be presented. The change in Esophageal endoscopy scores between two treatment groups will be examined using a two sample Student's t-test or Mann-Whitney test.

Eosinophilic Esophagitis Symptom Score

Improvement in symptom scores will be defined as a decrease in total symptom scores of two or more from baseline to end of treatment. Subjects will be categorized based on whether they improved their symptoms. Subjects who improved their symptom scores were considered as responders and patients who did not improve their symptom scores were considered as non-responders. The percentage of responders between the active treatment group and placebo group will be compared using Fisher's exact test. In addition, all of the summaries of severity of symptoms above will be repeated, split by responder/non-responder groups.

In addition, the change from baseline to end of treatment of the total symptom score and individual symptom scores (Abdominal/chest pain score, Vomiting score, and Dysphagia score) will be generated by treatment group and overall. The comparison of the change of individual symptom scores between the two treatment groups will be evaluated by using Fisher's exact tests.

The responses will be divided into three categories as suggested: Poor <30% improvement, good 30-70% improvement and excellent >70% improvement from baseline.

Percentage of subjects per response rate

The percentage of subjects showing an excellent response (≤ 1 eos/HPF), good response (2-14 eos/HPF), or poor response (≥ 15 eos/HPF) at the end of treatment will also be presented and analyzed between the two treatment groups using Fisher's exact test.

Eosinophilic Esophagitis Quality of Life Score

The Quality of Life score will also be reported for each treatment group at baseline and the end of treatment. The change from baseline to end of treatment will also be presented. The change in QOL scores between two treatment groups will be compared with two-sample t-test or Mann-Whitney test depending on the distribution of the change of the QOL score.

Combination Score:

Combination Score of four measures (Eosinophils/HPF, EREFS, investigator assessment and parental assessment of symptoms) will be calculated at baseline, end of treatment and end of study. The combination score will be calculated as (maximum eosinophils per high power field) + [10*esophageal endoscopy score (EREFs)] + [2* Parent assessment of esophageal symptoms (PEESS)] + [5*investigator assessment of EoE symptom activity]. The change from baseline to end of treatment will also be presented. The change in QOL scores between two treatment groups will be compared with two-sample t-test or Mann-Whitney test depending on the distribution of the change of the QOL score.

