11.12 Eosinophilic Esophagitis Symptom Score

Symptoms of Eosinophilic Esophagitis range from abdominal pain, gastroesophageal reflux, vomiting, and difficult swallowing. The symptoms will range from none to very severe as in Spergel⁵⁴. The symptoms will be in 3 categories and individual symptoms and total symptoms scores will be collected on a range of 0-4 (0-none, 1-mild, 2-moderate, 3-severe and 4-very severe).

Table 4: Eosinophilic Esophagitis Score

Symptoms	Score
Abdominal/Chest Pain	0-4
Vomiting/Regurgitation	0-4
Dysphagia	0-4
Total Score	0-12

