13.2 Sample Size Estimation

This is a pilot study in which we aim to identify efficacy of the Viaskin® Milk treatment. Sample size is based on projected subject volume. If efficacy is shown, our pilot data could be used to perform a power analysis for a larger study.

We will recruit 38 subjects and plan to have approximately 22 evaluable subjects with milk-induced EoE confirmed by endoscopy and biopsy.

A total sample size of 22 evaluable subjects (16 subjects in the active Viaskin® Milk group and 6 subjects in the placebo group) will achieve 90% power to detect a difference of 40 in mean maximum eosinophil counts between the two treatment groups (mean maximum eosinophil counts of 10 and 50 in Viaskin® Milk and in placebo, respectively) assuming that a common standard deviation is 20 using a two group *t*-test with a two-sided significance level of 0.05.

Approximately 22 subjects will be randomized to obtain 18 completed subjects with 10% drop-out.

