#### **3.2 Sample size determination and power calculation**

The primary objective of this study is to determine whether mean maximum eosinophil counts is different in the subjects on the Viaskin Milk group compared to those on the placebo group. This is a pilot study in which we aim to identify efficacy of the Viaskin® Milk treatment. Sample size is based on projected subject volume. If efficacy is shown, our pilot data could be used to perform a power analysis for a larger study. We will recruit 38 subjects and plan to have 22 evaluable subjects with milk-induced EoE confirmed by endoscopy and biopsy. Approximately 20 subjects (15 subjects in the active Viaskin® Milk group and 5 subjects in the placebo group) will be randomized to two treatment groups to obtain 18 completed subjects assuming 10% dropout rate. This sample size will have 90% power to detect a difference of 40 in mean maximum eosinophil counts between the subjects receiving Viaskin® milk (mean maximum eosinophil count of 10) and the subjects on placebo (mean maximum

eosinophil count of 50) assuming a common standard deviation of 20 using a two group *t*-test with a two-sided significance level of 0.05.

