#### **4.4.2.2 Eosinophilic esophagitis symptom and global assessment scores**

Summary statistics for individual eosinophilic esophagitis symptom score (Abdominal/Chest pain, Vomiting/Regurgitation, and Dysphagia) as well as investigator's eosinophilic esophagitis global assessment score at baseline, end of the double-blind treatment, and end of the open-label treatment as well as changes from baseline to end of the double-blind treatment and to end of the open-label treatment will be presented by treatment groups and overall (*Table 10*). The total EoE symptom score for each subject will be calculated and summary statistics at baseline, end of the double-blind treatment, and end of the open-label treatment, as well as the changes from baseline to end of the double-blind treatment and to end of the open-label treatment will be presented by treatment groups and overall. Improvement in symptom scores will be defined as a decrease in total eosinophilic esophagitis symptom score of two or more from baseline to end of the double-blind treatment and to end of the open-label treatment. Subjects will be categorized based on whether they improved their symptoms in two different ways. First, subjects who improved their symptom scores are considered as responders and subjects who did not improve their symptom scores are considered as non-responders. Second, subjects who improved their symptom scores will be categorized as poor improvement (<30%), good improvement (30-70%), and excellent improvement (>70%). RR or OR along with 95%

CI for the percentage of responders between two treatment groups will be presented. (*Table 11*).

In addition, frequency and severity EoE symptom scores measured by Pediatric Eosinophilic Esophagitis Symptoms Score (PEESS) will be examined. Summary statistics for the frequency and severity EoE symptom scores at baseline, end of the double-blind treatment, and end of the open-label treatment will be reported for each treatment group and overall. The changes in frequency and severity EoE symptom scores from baseline to end of the double-blind treatment and to end of the open-label treatment will be reported and Hodges-Lehmann estimates with 95% CIs for differences of medians of these changes between two treatment groups will be reported (*Table 12*).

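### The protocol tests change in each ordinal 0-4 symptom score with Fisher's exact test, which ignores the ordering and loses power against a shift; the synopsis and SAP name no such test

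*Protocol*

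**What the plan says.** **Protocol body.** Section 13.6.4.2: "The comparison of the change of individual symptom scores between the two treatment groups will be evaluated by using" Fisher's exact tests. Section 11.12 scores each symptom "on a range of 0-4 (0-none, 1-mild, 2-moderate, 3-severe and 4-very severe"). For neighbouring endpoints, section 13.6.4.2 names a t-test or Mann-Whitney test: change in endoscopy score and change in quality of life.

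**Protocol synopsis.** Changes in individual and total symptom scores are to be summarised descriptively. The same paragraph then promises group comparisons by t-test or Mann-Whitney for continuous variables and chi-square for categorical ones. It does not mention Fisher's test for these scores.

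**SAP.** Section 4.4.2.2 offers "Summary statistics for individual eosinophilic esophagitis symptom score (Abdominal/Chest pain, Vomiting/Regurgitation, and Dysphagia") and names no test for them. Table 10 lists change in order from -4 to +4 as counts and percentages. The Table 11 footnote gives the total symptom score, which is the sum of the same three items, a Hodges-Lehmann median difference between groups.

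**Versions.** The SAP is written from protocol 7.0, and the current protocol is 8.0. The SAP neither repeats nor withdraws the Fisher sentence.

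**The concern.** A treatment effect on a severity item is naturally a shift: one arm worsens less, or improves more, than the other. Fisher's test on a table with two columns and several rows gives the same p-value if the rows are shuffled. It cannot tell a set of changes that moves consistently one way from one that is merely different. With six placebo subjects there is little information to spare.

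The exception is also unexplained. Other change scores in the same protocol section get a test that can use order, and the SAP gives Hodges-Lehmann estimates to the endoscopy, PEESS, quality-of-life, composite and total symptom scores. Only the three components of the symptom total have no ordered comparison. Because the three texts differ, an analyst could run Fisher's test, run some other test, or run none, and cite the plan each time.

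**Working it through.** **Inputs**
- Group sizes: "A total sample size of 22 evaluable subjects (16 subjects in the active Viaskin® Milk group and 6 subjects in the placebo group"). The SAP, section 3.2, instead has "15 subjects in the active Viaskin® Milk group and 5 subjects in the placebo group". For completers, the protocol says "Approximately 22 subjects will be randomized to obtain 18 completed subjects with 10% drop-out"; at 3:1, 18 splits as 13.5 to 4.5, so 14 versus 4 was taken as the small case.
- Scale: 0 to 4, so change has 9 possible ordered values.
- Significance level: two-sided 0.05. This is stated for the primary analysis and assumed here.
- Distribution of change: not given anywhere. Everything below on size is therefore an assumption, shown as a range.

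**The plan's own figure.** None exists for this comparison. The only stated power, 90%, belongs to the primary t-test. With 16 versus 6 the noncentrality is 40 / (20 × √(1/16 + 1/6)) = 4.18 on 20 df, which gives 97.8%. That mismatch is a separate matter and does not bear on this point.

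**Why order is lost.** Let category k hold n_k subjects, b_k of them on placebo. With margins fixed, the table has probability Π C(n_k, b_k) / C(22, 6), where C(22, 6) = 74,613. Fisher's p-value sums the probabilities of all tables no more likely than the one observed. The product does not depend on how the categories are arranged. The rank test uses W, the sum of placebo midranks, and refers |W − 69| to the same 74,613 allocations, where 69 = 6 × 23 / 2. W does depend on the arrangement.

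**Simulation.** There were 2,000 trials per scenario, so the Monte Carlo standard error is at most √(0.25/2000) = 1.1 points. Fisher's test in its r × c (Freeman-Halton) form was compared with the exact midrank Wilcoxon-Mann-Whitney test at 16 versus 6.

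| Range of change | SD | Shift (SD) | Fisher % | Rank test % | Loss (points) |
|---|---|---|---|---|---|
| -4..+4 | 0.8 | 1 | 23.5 | 40.0 | 16.5 |
| -4..+4 | 1.0 | 1 | 22.2 | 45.4 | 23.2 |
| -4..+4 | 1.5 | 1 | 18.4 | 47.8 | 29.4 |
| -4..+4 | 0.8 | 1.5 | 52.0 | 77.8 | 25.8 |
| -4..+4 | 1.0 | 1.5 | 46.9 | 77.2 | 30.3 |
| -4..+4 | 1.5 | 1.5 | 41.7 | 80.3 | 38.6 |
| -2..+2 | 0.8 | 1.5 | 51.2 | 75.8 | 24.6 |
| -2..+2 | 1.5 | 1.5 | 63.8 | 79.3 | 15.5 |
| -1..+1 | 0.8 | 1.5 | 68.0 | 74.0 | 6.0 |
| -1..+1 | 1.0 | 1 | 35.9 | 42.7 | 6.8 |

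Shifts from 0.5 to 2.5 SD were run. The loss shrinks towards zero when the shift is small or when both tests are near 100%; the smallest was 0.4 points.

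**Skewed case.** Change took values 0 to 3, with 50% to 80% of active subjects unchanged and 10% to 30% of placebo subjects unchanged. Losses over four such pairs were 2.8 to 10.6 points across 16 versus 6, 15 versus 5 and 14 versus 4. For example, Fisher had 62.2% and the rank test 67.4% in one pair at 16 versus 6, and 54.0% and 64.6% in another.

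**Type I error.** Fisher 3.7% to 4.5%; exact rank test 2.8% to 5.0%. The gain does not come from a liberal test.

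**Counter-case.** In one artificial pure-spread scenario (all active subjects unchanged, placebo split evenly between one step up and one step down), Fisher had 89.3% and the rank test 22.0%.

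**The case against.** The best defence is that Fisher's test may never be run. The protocol leaves detailed methods to the SAP; the SAP names no test for these items, and the synopsis describes them only. The total symptom score already has an order-respecting estimate. With so few subjects, a frequency table for heavily tied items is a reasonable choice. Much of this stands, and it is why descriptive-only is offered below as an acceptable outcome. It does not remove the point, because the sentence is still in the current protocol and the SAP, built on the previous version, does not withdraw it.

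A second defence is that the text does not say Fisher's test is applied to the raw nine-value change; the next sentence of the protocol groups responses as poor, good or excellent. In the SAP, however, that grouping belongs to the total score. If grouped change were meant, three ordered categories would still be treated as unordered. The loss would then probably be nearer the small end of the range.

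A reader might also infer more than the documents support:
- **A fixed loss, such as 20 points.** No distribution of change is given, and the results run from almost nothing to nearly 40. The largest values are maxima over assumed scenarios, not bounds.
- **An invalid test.** Fisher's test holds its type I error; the defect is inefficiency.
- **A fault in the responder comparison.** Fisher's test is a usual choice for that binary endpoint.
- **That a rank test would rescue these endpoints.** At a 1 SD shift on the full range its own power is only 40% to 48%.

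**Conclusion.** The point holds as a minor one. The protocol assigns an unordered test to an ordered change score, and in every shift scenario run this cost power at 16 versus 6. The loss was about 0 to 39 points overall, at most 6 to 7 points when change was confined to -1..+1, and 3 to 11 points in the skewed scenarios. The small end is plausible, because baseline follows a milk-free period and many subjects may then have few symptoms to change from. These figures rest entirely on assumed distributions and on the effect being a shift.

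The reach is three secondary component scores. The primary endpoint and the total symptom score are untouched. The disagreement between synopsis, protocol body and SAP needs no assumption and should be settled whatever view is taken of the test.

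**What to change.** Choose one of two routes, before database lock:

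1. **Keep a comparison.** In protocol 13.6.4.2, replace Fisher's test for the individual items with the exact midrank Wilcoxon-Mann-Whitney test. In the SAP, name that test in 4.4.2.2 and add the Hodges-Lehmann difference with 95% CI to Tables 10-1 to 10-3, keeping the frequency counts. Bring the synopsis into line.
2. **Describe only.** Delete the Fisher sentence from 13.6.4.2 and say in both documents that these three items are summarised without a test.

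Either route is a wording change and needs no new data. Route 1 has a small price: the rank test is weaker than Fisher's for a pure difference in spread, and the Hodges-Lehmann estimate can be exactly zero when ties are heavy, which is why the counts should stay beside it.
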